## **Statistical Analysis Plan**

---

observed data is found not to follow a normal distribution, non-parametric methods may be employed (such as Wilcoxon rank sum test as appropriate).

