## **12.8 General Statistical Methods**

Standard statistical methods will be employed to analyze all data. All data collected in this study will be documented using summary tables and subject data listings. Unless otherwise noted, all p-values will be considered significant at a two-sided significance level of 5%. Continuous variables will be summarized using descriptive statistics, including count, mean, median, standard deviation (SD), minimum and maximum. Where appropriate, 95% two-sided confidence intervals for the means or medians will be presented. If the observed data are found not to follow a normal distribution, appropriate non-parametric methods may be employed. Categorical variables will be summarized by frequencies and percentages. Unless explicitly stated otherwise, percentages will utilize a denominator corresponding to the number of unique subjects.

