### **2.6 RANDOMIZATION**

This is a single-arm, multicenter, prospective clinical study where all eligible subjects will use the investigation device. Subjects will not be randomized.

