### 4.1 SAMPLE SIZE

This is a single-arm, multi-center, prospective study. The sample size is not hypothesis-driven and was chosen to provide adequate information on the investigational device's safety and performance. As such, the study plans to enroll up to 48 subjects to obtain a minimum of 36 evaluable subjects equally distributed across two age cohorts (6-13.9 years and 14-70 years).

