### 4.2 PRIMARY ANALYSIS

There are no pre-specified hypotheses associated with the primary effectiveness endpoints. Summary statistics will be presented by age cohort for all endpoints, stratified by time points of interest (e.g., day, night, overall). The primary effectiveness endpoints will be summarized for modified Intention to Treat (mITT) and Per Protocol (PP) analysis sets, where the percentage of TIR during ST phase will be compared to the percentage of TIR during HCL BG challenge days, HCL non-challenge days, and over the entire HCL.

Since the target BG challenges require a specific setpoint, the start of the challenge will be the first record at the given setpoint, and the end of the challenge will be last record at the same setpoint.

All statistical comparisons will be conducted at a two-sided significance level of 5% using a paired t-test. If the assumptions for parametric test are grossly violated, a non-parametric method such as Wilcoxon signed rank test may be used. Since the results of endpoint analyses will not be used to support clinical claims, no adjustment for multiplicity will be performed.

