### 7.6 OTHER DATA SUMMARIES

The distribution of each baseline characteristic or demographic parameter of interest (such as age, gender, medical history, etc.) will be presented. Data on all enrolled subjects will be presented. If a considerable number of subjects do not enter the HCL phase of the study, these results may also be presented for the mITT and/or PP analysis sets. Continuous variables will be summarized using count, mean, median, standard deviation, and range. Categorical variables will be summarized using counts and percentages.

Statistical testing will be performed to assess significant change from Baseline in various measures. Any testing performed will be based on one-sample t-test for continuous variables, or chi-square test or Fisher's exact test for categorical variables, using a two-sided significance level of 5%. If the

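### SAP 7.6 tests within-subject change from Baseline but names tests for independent samples: Wilcoxon rank sum as the only example fallback, and Fisher's exact for categorical data

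*SAP*

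**What the plan says.** SAP 7.6 (Other Data Summaries) states the purpose of its tests: "Statistical testing will be performed to assess significant change from Baseline in various measures". It does not list the measures.

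It then names the tests:
- **Continuous:** "Any testing performed will be based on one-sample t-test for continuous variables".
- **Categorical:** a chi-square test or Fisher's "exact test for categorical variables, using a two-sided significance level of 5"%.
- **Not normal:** "non-parametric methods may be employed (such as Wilcoxon rank sum test as appropriate").

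On design, SAP 2.6 says that "all eligible subjects will use the investigation device. Subjects will not be randomized". For the primary effectiveness endpoints, SAP 4.2 specifies a paired t-test and, if its assumptions fail badly, says that "a non-parametric method such as Wilcoxon signed rank test may be used". SAP 6.5 names the same fallback for the secondary effectiveness endpoints. Protocol 12.8 names no test: "If the observed data are found not to follow a normal distribution, appropriate non-parametric methods may be employed".

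**The concern.** With one arm, a change from Baseline has no second group to be compared with. Each subject supplies both values, and the two values are usually correlated. A one-sample t-test on the change scores respects that. The rank sum test does not: it treats the two sets of values as coming from different people. It is the non-parametric counterpart of the two-sample t-test. The counterpart of the one-sample or paired t-test is signed rank, which SAP 4.2 and 6.5 name.

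The categorical sentence has the same fault and is firmer, because it states what testing will be based on and offers no alternative. Fisher's exact test on the two margins ignores the pairing. The chi-square test is ambiguous: McNemar's statistic is a chi-square and fits, while Pearson's does not. With about 18 subjects per age cohort, sparse tables are plausible, and the only exact test named is the unpaired one.

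What is at stake is the error rate and power of whatever is tested under 7.6. With positive within-subject correlation, the unpaired tests reject too rarely under the null and usually lose power. With negative correlation, which is unlikely for repeated measures but not excluded by the documents, they would reject too often.

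**Working it through.** The plan gives no power figure to reproduce, because its sample size is not hypothesis-driven. The check is a reading of the text followed by an illustration.

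**Text, side by side**

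| Section | Comparison | Parametric test | Non-parametric example |
|---|---|---|---|
| SAP 4.2 | Standard therapy v closed-loop, same subjects | Paired t | Signed rank |
| SAP 6.5 | Same | Parametric test, not named | Signed rank |
| SAP 7.6 | Change from Baseline, same subjects | One-sample t | Rank sum |

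Only the last row names a test for independent samples. No between-group test is specified that would explain it: SAP 4.3 plans no separate analyses of Groups 1 and 2 and leaves other subgroups optional.

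**Inputs.** From the documents: two-sided 5%, and n = 18 (one age cohort), 36 (minimum evaluable) or 48 (maximum enrolled), since "the study plans to enroll up to 48 subjects to obtain a minimum of 36 evaluable subjects". Assumed: within-subject correlation (rho), distribution, size of shift, and categorical proportions.

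**Type I error, continuous.** An unpaired test takes the variance of the difference in means as 2σ²/n. For paired values the true variance is 2σ²(1 − rho)/n. A large-sample test that rejects beyond 1.96 therefore has true size 2Φ(−1.96/√(1 − rho)). At rho = 0.5 this is 2Φ(−2.77) = 0.6%. Simulation of the rank sum test itself (10,000 samples per setting, normal and lognormal data, all three n) agrees:

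| rho | Formula | Rank sum, simulated |
|---|---|---|
| −0.3 | 8.6% | 7.6–8.6% |
| 0 | 5.0% | 4.4–5.1% |
| 0.3 | 1.9% | 1.9–2.2% |
| 0.5 | 0.6% | 0.6–0.8% |
| 0.7 | 0.03% | 0.0–0.2% |

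Signed rank stays at 3.9–5.4% throughout.

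**Power, continuous, rho = 0.5, shift 0.5 SD** (for the proportional lognormal case, 0.5 SD on the log scale; log-SD 0.8)

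| Data | n | Rank sum | Signed rank |
|---|---|---|---|
| Normal | 18 | 23% | 47% |
| Normal | 36 | 54% | 81% |
| Normal | 48 | 71% | 91% |
| Lognormal, proportional shift | 36 | 54% | 75% |
| Lognormal, additive shift | 36 | 97% | 95% |

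Over rho of 0.3, 0.5 and 0.7, the extremes at this shift are a gain for rank sum of 69% v 59% (n = 18, lognormal additive, rho 0.3) and a loss of 20% v 68% (n = 18, normal, rho 0.7).

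**Categorical, one worked table.** Suppose 10 of 36 subjects are positive at Baseline and 17 of 36 later, with 1 subject changing from positive to negative and 8 the other way (10 − 1 + 8 = 17).
- Exact McNemar: 2 × (1 + 9)/2⁹ = 20/512, p = 0.039.
- McNemar chi-square, uncorrected: (8 − 1)²/9 = 5.44, p = 0.020.
- Pearson chi-square on the margins, uncorrected: 2.90, p = 0.088.
- Fisher's exact on the margins: p = 0.144.

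The same data are significant or not according to the test chosen.

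**Categorical, simulated** (20,000 samples of 36 pairs). For 20% at Baseline and 40% later with phi = 0.5, power is 31% for Fisher, 45% for Pearson, 62% for exact McNemar and 75% for uncorrected McNemar. With no change (both proportions 20% or both 40%) and phi of 0.3 to 0.5, type I error falls from 0.9% to 0.2% for Fisher and from 2.2% to 0.5% for Pearson. It is 4.1–4.7% for uncorrected McNemar and 1.1–2.6% for exact McNemar. At phi = −0.2, Pearson rises to 7.0–7.3%.

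**The case against.** The strongest reply is that nothing in the plan forces the wrong test. The fallback sentence is permissive: it offers rank sum as an example and leaves suitability to the analyst. The default one-sample t-test is right, and the Protocol asks only for suitable methods. This stands for continuous data. It does not cover the categorical sentence, which is not permissive.

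A second reply is that little depends on 7.6. SAP 4.2 and 6.5 already name signed rank for effectiveness, SAP 5.4 keeps safety descriptive, there are no success criteria, and the endpoint results are not meant to support clinical claims. All of this stands and limits the weight of the point. The SAP also does not say which measures 7.6 covers. Candidates are those collected both before and at the end of closed-loop use (the repeated questionnaires in Protocol Table 3, weight, vital signs, and the Clarke score with its cut-off of 4), but assigning them to 7.6 is inference.

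A third reply is that every input except n is assumed, that positive correlation makes the error conservative, and that the power difference can change sign. This too is correct, so the figures show direction and possible size only.

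Finally, exact McNemar is itself conservative in small samples. At n = 36, margins of 20% and phi = 0.3, its type I error was 1.9%, against 2.0% for Pearson. Its advantage is power, not nominal size.

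**Conclusion.** The point holds as a minor error in naming tests. For non-normal data, SAP 7.6 gives as its only example a test that does not suit its own stated purpose. For categorical change it names one unpaired test and one ambiguous one. No analysis receives conflicting instructions, since 4.2 and 6.5 govern other endpoints. Their wording suggests that rank sum in 7.6 is a slip.

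If the unpaired tests were actually used, the cost would depend on the within-subject correlation and the shape of the data, neither of which the documents give. Under normal data and positive correlation the loss of power is substantial; under an additive shift in skewed data it can vanish or reverse. No expected loss for this study can be stated. The primary, secondary and safety endpoint analyses are unaffected.

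**What to change.** In SAP 7.6:
- State that the one-sample t-test is applied to within-subject change scores, and replace Wilcoxon rank sum with Wilcoxon signed rank as the fallback for change from Baseline.
- For within-subject change in a binary variable, name McNemar's test, in its exact version if the discordant pairs are few. For more than two categories, name a test of marginal homogeneity.
- Keep rank sum, Pearson chi-square and Fisher's exact only for any comparison between subgroups, and say so.

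This costs one or two sentences of SAP text. Data collection, sample size and the endpoint analyses do not change.

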### **7.7 STATISTICAL SOFTWARE**

The statistical software package SAS® 9.4 or later will be used for all the data derivations, summarization, data listings and statistical analyses. Additional statistical software may be used for graphics or validation purposes as appropriate.

### **7.8 PERIODIC REVIEW OF CONTROLLER DATA**

Following the upload of controller data into the database, the data will be made available to Sponsor representatives for periodic reviews. Reviews of the controller data will be conducted to identify any anomalies and to confirm the algorithm appears to be functioning as expected. These reviews, including any findings, will be documented. Unless potential safety concerns are identified, the results of such reviews will not be shared with study sites or subjects, and will not affect the data analyses.
